| 15. | 
Obtain Reference Glucose Values using the Nova StatStrip Hospital Glucose Meter System every 10-60 minutes from time 4 to 32 hours according to the following guidelines:
 
A. Every 10 minutes: Monitor the subject's Reference Glucose Values every 10 minutes whenever either of the following occur:
 
I. Either of the Dexcom G6 CGM's is less than 70 mg/dL.II. When the most recent Reference Glucose Value is less than 70 mg/dL. 
Discontinue every 10 minute Reference Glucose Value monitoring when both of the following have occurred:
 
I. Both Dexcom G6 CGM's are greater than 70 mg/dL.II. The subjects have two consecutive Reference Glucose Values greater than 70 mg/dL. These Reference Glucose Values will be measured by the Nova StatStrip Hospital Glucose Meter System on either a venous or capillary blood sample. 
B. Every 30 minutes: Monitor the subject's Reference Glucose Values every 30 minutes when the following occur:
 
I. After both Dexcom G6 CGM's begin to return glucose readings after their original insertion and prior to the onset of the closed loop glucose control session, for purposes of verifying the accuracy of the CGM's. This monitoring prior to the onset of the closed loop glucose control session may be discontinued once both CGM's have met the following CGM Validation Criteria on two consecutive Reference Glucose Values: 
CGM readings must be within ± 20 mg/dL of the Reference Glucose Value for CGM readings < 100 mg/dL or CGM readings must be within $\pm 20\%$ of Reference Glucose Values for CGM readings ≥ 100 mg/dL on two consecutive Reference Glucose Values.
 
II. During the first 2 hours of the closed loop glucose control session (time 5-7 hours).III. When either Dexcom G6 CGM has a glucose reading less than 85 mg/dL displayed on either the Dexcom G6 Receiver or the Dexcom G6 Follow App.IV. During periods of severe hyperglycemia, which is defined as a CGM or Reference Glucose Value greater than 240 mg/dL.V. When only one Dexcom G6 CGM is available for use by the FUSION system for glucose control.VI. After a CGM has been replaced, and until the replaced CGM has met the above noted CGM Validation Criteria.VII. When the subject experiences any signs of neuroglycopenia, regardless of the glucose level displayed by the CGM's.VIII. From time 29-32 hours, which is the 3 hour time period after conclusion of the closed loop glucose control session. |
|-----|---|

| | |
|-----|--|
| | 
C. Every 60 minutes: Monitor the subject's Reference Glucose Value every 60 minutes when the following occur:
 
During the last 22 hours of the closed loop glucose control session (time 7-29 hours), if the following occur:
Both CGM's are in the range of 85-240 mg/dL and the subject is not experiencing any signs of neuroglycopenia. 
Result: _____ mg/dL, Time: _____ (24 hour clock) Note: Notify study team if the CGM or Reference Glucose Value is < 70 mg/dL or > 300 mg/dL.
 |
| 16. | 
Dexcom G6 CGM Placement, Calibration and Replacement
 
Visit 3 (Time 0 to 5 hours): Place two Dexcom G6 CGM's in the abdomen 5 cm to the right and left of the umbilicus (Figure 28).
  
18 years and older
 
Figure 28 – Green shaded areas denote appropriate areas of the abdominal wall to place the Dexcom G6 CGM's. This figure is from the Dexcom G6 CGM user manual.
 |

Make sure the Dexcom G6 Transmitters are labeled “#1” and “#2”. These labels should be in a clearly visible position after the Transmitters have been attached to the Dexcom G6 glucose sensors. Once both Dexcom CGM’s begin to return glucose values, obtain a Reference Glucose Value using the Nova StatStrip Hospital Glucose Meter System. If either of the Dexcom CGM’s do not meet CGM Validation Criteria, they may be calibrated. The Dexcom G6 CGM’s must meet the following CGM Validation Criteria throughout the CRC study session (visit 3), otherwise they will be calibrated as often as is necessary:

1. CGM readings must be within ± 20 mg/dL of the Reference Glucose Value for CGM readings < 100 mg/dL or CGM readings must be within $\pm 20\%$ of Reference Glucose Values for CGM readings ≥ 100 mg/dL on two consecutive Reference Glucose Values.

Calibrations should only be attempted when the glucose rate of change is less than ± 2 mg/dL/min on the Dexcom G6 CGM (see figure 29).

If after two calibration attempts prior to beginning the closed loop glucose control session (time 0-5 hours) the CGM(s) still do not meet CGM Validation Criteria, they may be replaced. The closed loop glucose control session may not begin until there are two working Dexcom G6 CGM’s in place, and both CGM’s have met the above noted CGM Validation Criteria.

Closed Loop Glucose Control Session (Time 5 to 29 hours):

Inspect the CGM sites (see Monitoring Activities) and ensure proper performance and communication to the two Dexcom G6 Receivers that are labeled “#1” and “#2”, and that are part of the FUSION system (Figure 20); ensure communication with the Dexcom G6 Follow APP on the two mobile phones labeled “#1” and “#2”. The CGM’s may be replaced during the closed loop glucose control session for any of the following reasons:

1. The CGM(s) do not meet the above noted CGM Validation Criteria and are unable to be calibrated after two attempts over a two-hour period of time.
2. If the CGM measurement is > 180 mg/dL and the simultaneous (e.g., within 5 minutes) Reference Glucose Value is < 100 mg/dL, the CGM may be replaced as this scenario may lead to inadvertent insulin administration by the FUSION system, which may result in hypoglycemia (< 70 mg/dL).
3. If the CGM measurement is < 100 mg/dL and the simultaneous (e.g., within 5 minutes) Reference Glucose Value is > 180 mg/dL, the CGM may be replaced as this scenario may lead to a delay in the treatment of hyperglycemia, which will increase the risk for DKA in type 1 diabetic subjects.

Trend Arrow: Steady

Changing:

- Less than 1 mg/dL each minute
- Up to 15 mg/dL in 15 minutes

Trend Arrow: Slowly Rising or Falling

Changing:

- 1 – 2 mg/dL each minute
- Up to 30 mg/dL in 15 minutes

Figure 29 – Glucose rate of change, as noted by the Dexcom G6 CGM trend arrows.

| | |
|-----|---|
| | 
4. The CGM(s) experience repeated compression artifact that is unable to be relieved through repositioning of the subject. Compression artifact is a sudden non-physiologic fall in one of the CGM glucose levels (e.g., $< \pm 2$ mg/dL/min), when the second CGM does not experience this same degree of fall in its glucose level. The FUSION system monitors for compression artifact and will display an alarm alerting the clinical study nurse of its occurrence, and the need to reposition the subject so that they are not directly laying on the transmitter/sensor pair.
 
5. The subject is experiencing significant bleeding, pain, or signs of infection at the CGM insertion site.
 
6. The CGM transmitter/sensor pair stops working for any reason.
 
If the Dexcom G6 CGM's need to be replaced during visit 3, the preferred replacement site is another abdominal position (see Figure 28). If another abdominal site is used, place the new CGM at least 10 cm away from the other abdominal CGM that is still working properly. As an alternative, and only if another abdominal site is not available or may result in further compression artifacts, a replacement CGM may be placed in the posterior upper arm position, on the contralateral side from the remaining CGM (e.g., if remaining CGM is on the right side of the abdomen, place the replacement CGM on the posterior aspect of the left upper arm). In the event a replacement CGM is used, it must be calibrated until it meets the above noted CGM Validation Criteria. The position of the CGM's and all calibration attempts will be noted on the Case Report Form.
 |
| 17. | 
Frequency of CGM Calibration
 
The CGM's may be recalibrated as often as necessary during the closed loop glucose control session (time 5-29 hours) if they do not meet the following CGM Validation Criteria:
 
1. CGM's glucose readings must be within ± 20 mg/dL of Reference Glucose Values for CGM readings less than 100 mg/dL or must be within $\pm 20\%$ of Reference Glucose Values for CGM readings greater than 100 mg/dL.
 
Only CGM's not meeting the above noted CGM Validation Criteria will be calibrated, thus either one or both CGM's may be calibrated at any point in time, depending on the circumstances.
 
In addition, the FUSION system monitors the CGM's for signs of significant deviation (e.g., $> 20\%$) from the average glucose value used by the FUSION system for glucose control. If the FUSION system detects CGM deviation of $> 20\%$ from the average glucose value used by the FUSION system (e.g., CGM #1 = 70 mg/dL, CGM #2 = 130 mg/dL, and average glucose value used by the FUSION system = 100 mg/dL) it will display an alarm alerting the clinical study nurse of this occurrence, and request that both CGM's be recalibrated against a Reference Glucose Value.
 
To be clear, if the CGM's meet the above noted CGM Validation Criteria throughout their time of use in visit 3, and the FUSION system does not automatically call for a CGM calibration, it is possible to complete visit 3 with no calibration of either CGM.
 |

DEMONSTRATION OF AN ARTIFICIAL INTELLIGENCE BASED CLOSED LOOP GLUCOSE CONTROL SYSTEM AS A THERAPEUTIC MODALITY IN TYPE 1 AND TYPE 2 DIABETIC PATIENTS

Protocol IMT 2022-1

CONFIDENTIAL

Version1.0.7

22 August 2022

| | |
|-----|--|
| | |
| 18. | 
Standard Blood Collection Protocol per CRC guidelines
 
RN: Draw blood glucose sample from retrograde intravenous line: Draw 0.5 mL of whole blood to measure glucose levels using the Nova StatStrip Hospital Glucose Meter System every 10-60 minutes (time 4 to 32 hours).
 |
| 19. | 
Meal Challenge Protocol
 
Time 5 hours (~1200 on day 1): Subject to consume lunch with 60 grams of carbohydrate.
 
Time 11 hours (~1800 on day 1): Subject to consume dinner with 75 grams of carbohydrate.
 
Time 25 hours (~0800 on day 2): Subject to consume breakfast with 50 grams of carbohydrate.
 
Carbohydrates should make up 45-60% of the total Kcal's of each meal.
 
Time 5 to 29 hours: Closed loop control of blood glucose with FUSION system (Figure 20), to control range of 100-140 mg/dL.
 
Throughout the entirety of the subjects stay in the CRC (e.g., time 0 to 32 hours), if the subject has a Reference Glucose Value less than 70 mg/dL or is experiencing signs of neuroglycopenia (hypoglycemia of sufficient duration and degree to interfere with normal brain metabolism and function) at any Reference Glucose Value, they will be offered snacks and/or glucose containing juice.
 |
| 20. | 
RECOVERY PERIOD (Time 29 to 32 hours)
 
1. Type 1 Diabetic Subjects:
 
Type 1 diabetic subjects will be required to have four consecutive Reference Glucose Values within the range of 80-250 mg/dL, with the most recent rate of change being less than ± 2 mg/dL/min, which is equal to either a single sideways arrow or a single up or down arrow as noted in the illustration above (Figure 29), which was taken from Dexcom G6 CGM manual.
 
The glucose sample source can be either from a venous catheter sample, or from a capillary fingerstick. The Nova StatStrip Hospital Glucose Meter System will be used to analyze the sample for glucose.
 
Following standard practice, subjects with type 1 diabetes will receive a dose of basal insulin dose two hours before discontinuation of the FUSION systems continuous insulin infusion (CII), as it is expected that basal insulin levels will slowly reach a therapeutic level after administration. An endocrinologist ([name] or [name]) will determine the dose of the basal insulin before CII discontinuation for subjects with type 1 diabetes. The next dose of basal insulin (at home) and transition to the participants home regimen will be determined by [name] or [name].
 |

The study's principal investigators ([name] or [name]) will determine the short acting insulin dose to cover the lunch (60 grams of carbs) that is consumed at approximately 1200 hours on Day 2, based on the participant's medical history, pre-prandial Reference Glucose Value that is measured by the Nova StatStrip Hospital Glucose Meter System, and carbohydrate load in the meal.

Subjects using insulin pumps will start continuous subcutaneous insulin therapy with rapid acting insulin immediately after stopping the FUSION systems CII. [name] or [name] may adjust the settings of the subject's insulin pump prior to discharge from the CRC to minimize the risk of hypoglycemia or DKA.

2. Type 2 Diabetic Subjects:

Type 2 diabetic subjects will be required to have four consecutive Reference Glucose Values within the range of 80-250 mg/dL, with the most recent rate of change being less than ± 2 mg/dL/min, which is equal to either a single sideways arrow or a single up or down arrow as noted in the above illustration (Figure 29).

The glucose sample source can be either from a venous catheter sample, or from a capillary fingerstick. The Nova StatStrip Hospital Glucose Meter System will be used to analyze the sample for glucose.

Recovery Period (Time 29 to 32 hours) – Subject to resume subcutaneous insulin injections:

- i. Subjects routinely injecting long acting insulin only in the morning will take a dose of long acting insulin at 2/3 of their normal dose. ____ units given at ____ : ____ (24 hour clock).
 - i. Subjects routinely injecting long acting insulin morning and evening will take a dose of long acting insulin at $\frac{1}{2}$ their normal morning dose and be instructed to take their evening dose as usual. ____ units given at ____ : ____ (24 hour clock).
 - ii. Subjects routinely injecting long acting insulin only in the evening will take a dose of long acting insulin at 1/3 of their normal dose and be instructed to take their evening dose as usual.
____ units given at ____ : ____ (24 hour clock).
 - iii. The study's principal investigators ([name] or [name]) will determine the short acting insulin dose to cover the lunch (60 grams of carbs) that is consumed at approximately 1200 hours on Day 2, based on the participant's medical history, pre-prandial Reference Glucose Value that is measured by the Nova StatStrip Hospital Glucose Meter System, and carbohydrate load in the meal.

| | |
|------------|--|
| | 
Both type 1 and type 2 diabetic subjects will consume a lunch consisting of 60 grams of carbohydrates beginning at 1200 hours on day 2.
 
The study nurse will check Reference Glucose Values every 30 minutes with the Nova StatStrip Hospital Glucose Meter System – Times 29, 29.5, 30, 30.5, 31, 31.5, and 32 hours, etc., until the subjects Reference Glucose Values are in the range of 80-250 mg/dL for a period of at least two hours after the completion of the closed loop glucose control session, and the most recent glucose rate of change is less than \pm 2 mg/dL/min.
 
If the subject is removed from the study early due to the presence of hypoglycemia (e.g., < 54 mg/dL or < 70 mg/dL with neuroglycopenic symptoms) or for any other reason, they will have ongoing monitoring in the CRC until they have had glucose values in the range of 80-250 mg/dL for a period of at least two hours, and until their most recent glucose rate of change is less than \pm 2 mg/dL/min. In the event the subject is removed from the study early, any short or long acting insulin dosing needed from the time the subject is removed from the study until the time the subject is discharged from the CRC, will be per the orders of the study's principal investigators ([name] or [name]).
 
If the subjects CGM or Reference Glucose Values are less than 70 mg/dL at the time they are removed from the study, they will have Reference Glucose Values measured every 10 minutes until such time as their glucose values are greater than 70 mg/dL. If the subject develops signs of diabetic ketoacidosis (e.g., Reference Glucose Value > 240 mg/dL and blood ketones > 1 mmol/L), they will have a basic metabolic panel, venous pH, and beta hydroxybutyrate drawn. If the subject develops diabetic ketoacidosis, they will be stabilized and have ongoing care per the usual routine of Emory Healthcare.
 |
| 21. | 
Intravenous Catheter Removal:
 
Remove both IV catheters once the subjects Reference Glucose Value is in the range of 80-250 mg/dL for a period of at least two hours after the completion of the closed loop glucose control session, and when the most recent glucose rate of change is less than \pm 2 mg/dL/min. This criterion will not be met prior to time 32 hours (\sim 1500 hours of 2nd day in the CRC). The subject may be discharged from the CRC unit once this criterion has been met.
 |
| 22. | 
Discharge Criteria
 
The subjects Reference Glucose Value must be between 80-250 mg/dL for a period of 2 hours before discharge, and their most recent glucose rate of change must be less than \pm 2 mg/dL/min. For subjects who have been placed back on their usual continuous subcutaneous insulin infusion pump, they may be discharged once their Reference Glucose Value is between 80-250 mg/dL for a period of 2 hours, and their most recent glucose rate of change must be less than \pm 2 mg/dL/min.
 |

DEMONSTRATION OF AN ARTIFICIAL INTELLIGENCE BASED CLOSED LOOP GLUCOSE CONTROL SYSTEM AS A THERAPEUTIC MODALITY IN TYPE 1 AND TYPE 2 DIABETIC PATIENTS

Protocol IMT 2022-1

CONFIDENTIAL

Version1.0.7

22 August 2022

| | |
|------------|--|
| | 
All subjects must be observed for a minimum of 3 hours after the conclusion of the closed loop glucose control session and for at least 60 minutes after their most recent subcutaneous insulin injection (subjects on MDI insulin therapy), before being discharged from the CRC.
 
End of Study Reference Glucose Value, BG: _____ mg/dL, Time: _____ (24 hour clock)
 |
| 23. | 
After the subjects have been discharged from the CRC, they will be instructed to check their blood glucose levels at home using their blood glucose meter at the following times:
 
1. On arrival at home.2. Before dinner.3. At 9 P.M.4. On awakening the next morning. 
Subject to call study coordinator with concerns they have about their glucose levels or any other issue.
 |

Attachment 1

Serious Adverse Event Report Form

IMT2022-1-A1

Serious Adverse Event

An adverse event is any untoward medical event associated with use of a drug or drug delivery system in humans, whether or not it is considered related to a drug or drug delivery system. For purposes of this study, a Serious Adverse Event (SAE) is any adverse event from this study that results in one of the following outcomes:

- Death
- A life threatening experience
- Persistent or significant disability/incapacity
- Seizure secondary to hypoglycemia
- Myocardial infarction that is temporally related to a hypoglycemic (<70 mg/dL) event
- Cardiac dysrhythmia that is temporally related to a hypoglycemic (<70 mg/dL) event
- Any other complication related to hypoglycemia
- Reference Glucose Value less than 54 mg/dL
- Considered significant for any other reason

Serious Adverse Event (SAE) Report Form

DEMONSTRATION OF AN ARTIFICIAL INTELLIGENCE BASED CLOSED LOOP GLUCOSE CONTROL SYSTEM AS A THERAPEUTIC MODALITY IN TYPE 1 AND TYPE 2 DIABETIC PATIENTS

Protocol Number: **IMT2022-1**

Site: _____

Pt ID: _____

1. SAE Onset Date: _____ (dd/mm/yyyy)
2. SAE Stop Date: _____ (dd/mm/yyyy)

3. Location of serious adverse event: _____

4. Was this an unexpected adverse event? Yes No

5. Brief description of participant(s) with no personal identifiers:
Sex: F M Age: _____

Diagnosis for study participation: _____

6. Brief description of the nature of the serious adverse event (attach description if more space needed):

7. Category of the serious adverse event:
○ Death – date ____/____/____ (dd/mm/yyyy)

DEMONSTRATION OF AN ARTIFICIAL INTELLIGENCE BASED CLOSED LOOP GLUCOSE CONTROL SYSTEM AS A THERAPEUTIC MODALITY IN TYPE 1 AND TYPE 2 DIABETIC PATIENTS

Protocol IMT 2022-1

CONFIDENTIAL

Version1.0.7

22 August 2022

- Complication from severe hypoglycemia
- Life-threatening
- Hospitalization- prolonged
- Disability / incapacity
- Required intervention to prevent permanent impairment

Other: _____

8. Intervention type:

Medication or Nutritional Supplement: specify _____

Device: Specify: _____

Surgery: Specify: _____

Behavioral/Life Style: Specify: _____

9. Relationship of event to intervention:

- Related** - The AE is known to occur with the study intervention, there is a reasonable possibility that the study intervention caused the AE, or there is a temporal relationship between the study intervention and event. Reasonable possibility means that there is evidence to suggest a causal relationship between the study intervention and the AE.
- Not related** - There is not a reasonable possibility that the administration of the study intervention caused the event, there is no temporal relationship between the study intervention and event onset, or an alternate etiology has been established.

10. Was study intervention discontinued due to event? Yes No

11. What medications or other steps were taken to treat serious adverse event?

DEMONSTRATION OF AN ARTIFICIAL INTELLIGENCE BASED CLOSED LOOP GLUCOSE CONTROL SYSTEM AS A
THERAPEUTIC MODALITY IN TYPE 1 AND TYPE 2 DIABETIC PATIENTS

Protocol IMT 2022-1

CONFIDENTIAL

Version1.0.7
22 August 2022

12. List any relevant tests, laboratory data, history, including preexisting medical conditions

13. Type of report:

Initial

Follow-up

Final

Signature of Principal Investigator: _____ Date: _____

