4.3.10 RISK OF DIABETIC KETOACIDOSIS (DKA)

DKA is a metabolic condition brought on by lack of sufficient insulin supply such that the body can no longer use glucose as a fuel source, which leads to excessive breakdown of fat, and abnormal labs consisting of elevated blood levels of glucose and beta hydroxybutyrate, with a concomitant lowering of the blood pH. The risk of the participants entering the study while they are in DKA will be mitigated by screening for ketones at the time they are admitted to the CRC on visit 3. This screening will include a capillary blood Reference Glucose Value measured on the Nova StatStrip Hospital Glucose Meter System and blood ketone levels measured on the Nova Max Plus ketone meter (Nova Biomedical).

The risk of the subjects developing DKA while they are in the study will be mitigated by obtaining Reference Glucose Values at least every 1 hour. If the subjects CGM or Reference Glucose Value is > 240 mg/dL, the subjects will have their blood screened for ketones using the Nova Max Plus ketone meter. If the subject's blood ketone level is > 1 mmol/L, they will have venous blood sent for a basic metabolic panel, pH, and beta hydroxybutyrate to determine if they are in DKA. Subjects who are found to be in DKA, during their stay in the CRC during visit 3, will be removed from the study.

The benefit of testing the FUSION system on type 1 and type 2 diabetic subjects, whose blood glucose levels are difficult to control, outweighs the risk of the subjects developing DKA, given the information on the FUSION systems performance that will be gathered during the course of this study.

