8.1.1.7 OTHER

Refer to Protocol 1 (IMT2022-1-P1) for other materials needed to complete the study.

Refer to Protocol 2 (IMT2022-1-P2) for meal challenge in diabetic subjects.

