DEMONSTRATION OF AN ARTIFICIAL INTELLIGENCE BASED CLOSED LOOP GLUCOSE CONTROL SYSTEM AS A THERAPEUTIC MODALITY IN TYPE 1 AND TYPE 2 DIABETIC PATIENTS

Protocol IMT 2022-1

CONFIDENTIAL

Version1.0.7

[figure not shown]
22 August 2022

To avoid risk to our human subjects, vital signs will be monitored closely. Frequent independent glucose measurements will be performed (every 10-60 minutes) to minimize the risk of severe hypoglycemia (< 54 mg/dL) or moderate hypoglycemia (54-69 mg/dL) with the above noted hypoglycemia symptoms. The protocol calls for rescue doses of 15 mL of 50% dextrose for severe hypoglycemia, moderate hypoglycemia with hypoglycemia symptoms, or neuroglycopenia. In addition, the study on any one subject will be terminated if they experience a severe hypoglycemia event (< 54 mg/dL). The overall study will be terminated if two subjects experience a severe hypoglycemia event (< 54 mg/dL).

Patients with a history of liver failure, renal failure, cerebrovascular accident, seizure disorder, congestive heart failure, and ischemic heart disease will not be recruited for this study.

During the time period when the FUSION system is operational and active, if a participant's CGM or Reference Glucose Value is >240 mg/dL for over 1 hour or ≥ 300 mg/dL at any point after starting the FUSION system, the following steps will be taken: Ketones will be assessed at the discretion of the principal investigator(s) for any concern about possible ketosis or DKA by checking a blood ketone level at the bedside. If the blood ketone level is greater than 1 mmol/L, a venous blood sample from the subject will be sent to the central laboratory of Emory Healthcare for a basic metabolic panel, blood pH, and beta hydroxybutyrate level. If the subject is found to be in DKA, the subject will be stabilized per the usual routine care at Emory Healthcare.

When a hyperglycemia/ketotic event meets the above reporting requirements, an Adverse Event Form will be completed. Events meeting DKA criteria should be considered serious adverse events with respect to reporting requirements. Hyperglycemia events not meeting criteria for DKA generally will not be considered as serious adverse events unless one of the severe adverse event criteria is met.

| Meal Challenge Protocol Detailed | | | | | | | | | |
|--|---|------|-----------------------------|-----------|----|-------|----|--------|----|

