| | 
Assess for the development of DKA, severe hyperglycemia (> 240 mg/dL), or HHS by obtaining Reference Glucose Values at least every 1 hour. The study will have termination criteria (see below) that will terminate the study on the subject if they are showing signs of DKA, severe hyperglycemia, or HHS.
 |

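### Protocol 2 leaves in-session ketone testing to discretion and, at 241–299 mg/dL, to more than 1 hour of hyperglycemia, while Section 4.3.10 requires a test at any value above 240 mg/dL

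*Combined protocol and SAP*

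**What the plan says.** Section 4.3.10, on subjects developing DKA during the study, is unconditional: "If the subjects CGM or Reference Glucose Value is > 240 mg/dL, the subjects will have their blood screened for ketones". If the meter shows more than 1 mmol/L, "they will have venous blood sent for a basic metabolic panel, pH, and beta hydroxybutyrate to determine if they are in DKA".

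For the session procedure, Section 8.1.1.7 sends staff elsewhere: "Refer to Protocol 2 (IMT2022-1-P2) for meal challenge in diabetic subjects". In Protocol 2, under Potential Problems, the trigger while the device is running is "CGM or Reference Glucose Value is >240 mg/dL for over 1 hour or ≥ 300 mg/dL at any point after starting the FUSION system". The step that follows is "Ketones will be assessed at the discretion of the principal investigator(s", tied to any concern about ketosis or DKA.

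Three numbered items of Protocol 2 also bear on this:

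- Item 13E: "Assess for the development of DKA, severe hyperglycemia (> 240 mg/dL), or HHS by obtaining Reference Glucose Values at least every 1 hour". It then points to the termination criteria for subjects showing signs of DKA.
- Item 15B, in its list of situations that move Reference checks to every 30 minutes: "During periods of severe hyperglycemia, which is defined as a CGM or Reference Glucose Value greater than 240 mg/dL".
- Item 15C: "Notify study team if the CGM or Reference Glucose Value is < 70 mg/dL or > 300 mg/dL".

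Individual termination criterion 5 (Section 9.1, repeated in Protocol 2 item 14A) requires a Reference value above 240 mg/dL together with blood ketones above 1 mmol/L. It has no duration condition.

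**The concern.** The two texts differ both on when a ketone test is prompted and on whether it is obligatory. Staff working from Protocol 2 could leave an excursion to 241–299 mg/dL untested if it lasts 1 hour or less. They could also leave a longer or higher one untested if the investigator saw no cause for concern.

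Without a ketone result, neither criterion 5 nor the confirmatory laboratory panel can be triggered. The glucose-only stops can end a session, but they do not identify ketosis. A DKA case also matters beyond the individual: under Section 9.2, criterion 3, one case after the start of closed loop ends the whole study. Two of the eight planned subjects have type 1 diabetes, and Protocol 2 item 16 itself links delayed treatment of hyperglycemia to DKA risk in that group.

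**Working it through.** The plan gives no figure to reproduce. The check sets the rules side by side and then applies interval arithmetic.

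**1. The two rules**

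| | Section 4.3.10 | Protocol 2, Potential Problems |
|---|---|---|
| Trigger, 241–299 mg/dL | First value above 240 | More than 60 min above 240 |
| Trigger, 300 mg/dL or more | Immediate | Immediate |
| Obligation | Mandatory | Investigator's discretion |

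**2. Does another Protocol 2 item order the test during closed loop?**

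- Item 7 orders ketone testing, but at admission.
- Item 13E assesses by Reference glucose and points to the termination criteria.
- Criterion 5 in item 14A needs a ketone result but does not order one.
- Item 15B changes only the Reference glucose interval.
- Item 15C sets a notification limit, which on the high side is 300 mg/dL.
- Item 20 describes the panel once ketones exceed 1 mmol/L, and again presupposes the result.

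None of them orders the test.

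**3. Timing illustration**

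Inputs: CGM values every 5 min (Section 4.3.1), Reference values every 30 min above 240 mg/dL (Section 4.3.11, item 15B), and a stop at more than 2 hours above 240 mg/dL (Section 9.1, criterion 4). Assumptions: glucose flat at 245 mg/dL from time 0, readings aligned to time 0, and no unscheduled checks.

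- Section 4.3.10: test at 0 min.
- Protocol 2, CGM values: first reading after 60 min is 60 + 5 = 65 min.
- Protocol 2, if only Reference values are above 240 mg/dL: 60 + 30 = 90 min.
- First Reference value after 120 min, when the stop would be confirmed: 120 + 30 = 150 min.

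**4. An excursion of exactly 60 min at 241–299 mg/dL**

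- CGM values: 60/5 + 1 = 13 per sensor.
- Reference values: 60/30 + 1 = 3.
- With two sensors: 2 × 13 + 3 = 29 readings.

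Up to 29 readings meet the Section 4.3.10 trigger, and none meets the Protocol 2 trigger.

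**5. Vital signs (secondary)**

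Section 10.2.2 requires them at least hourly during closed loop: 24/1 = 24 sets in 24 hours. Item 13A schedules them every 4 hours for the whole stay: 24/4 = 6 sets.

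**The case against.** The strongest reply is that Section 4.3.10 is binding and Protocol 2 does not forbid earlier testing, so a test at the first value above 240 mg/dL complies with both. Protocol 2 is not a standalone document, since it refers back to the main text. Item 13E leads on to criterion 5, which presupposes a ketone result. The 240 mg/dL CGM alarm in Section 4.3.11 alerts the nurse and staff, Reference checks move to every 30 minutes, and sessions stop after more than 2 hours above 240 mg/dL or more than 1 hour above 300 mg/dL. The principal investigator can also end the study on safety grounds. The timings in step 3 depend on an assumed grid, and nothing ties the 2-hour stop to a scheduled reading.

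Most of this stands, and it bounds the risk. It does not remove the conflict. The alarm and the 30-minute checks carry no ketone step in Protocol 2, and criterion 5 depends on a test that the session procedure leaves to judgment. Nor is this an open choice between two reasonable rules, because Section 4.3.10 and criterion 5 already commit the plan to the stricter one.

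On vital signs, the two intervals can be read as monitoring versus case report form recording. That reading is plausible, so this part is only a consistency edit.

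**Conclusion.** The conflict is real and should be corrected. For glucose that stays at 241–299 mg/dL, Protocol 2 delays even the consideration of a ketone test by more than 1 hour relative to Section 4.3.10, and an excursion of 1 hour or less prompts none. At 300 mg/dL or more there is no delay, only discretion. Harm requires staff to follow the Protocol 2 narrative in preference to Section 4.3.10 and, once its trigger is met, the investigator to see no concern. The documents give no rate of excursions above 240 mg/dL, so no expected number of missed tests can be stated.

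Three stronger readings are tempting, and the documents do not support them:

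- A reader might infer that the plan has no mandatory in-session ketone rule. It has one, in Section 4.3.10.
- A reader might infer that item 13E relies on glucose alone. It also points to the termination criteria.
- A reader might infer that subjects will be monitored too rarely for vital signs. Hourly checks satisfy both texts, and Section 8.1.1.4 requires a cardiac monitor, a pulse oximeter and blood pressure capability in the room.

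**What to change.** In Protocol 2, Potential Problems, replace the trigger and the discretionary sentence with a mandatory ketone meter test at the first CGM or Reference value above 240 mg/dL in each excursion during closed loop. State a repeat interval while glucose stays above 240 mg/dL, for example every 60 minutes. Cite the rule in item 13E. The repeat interval is needed, because a rule applied to every qualifying reading could be taken to demand up to 29 tests in the 60-minute excursion above.

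The cost is a wording amendment, brief retraining and a few extra fingerstick or line-sample tests. The meter and strips are already on the Protocol 1 materials list. As an illustration, assume 0–3 excursions per subject, at most one per study meal (overnight snacks could add more):

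- One test per excursion: 0–3 per subject, or 0–24 over 8 subjects.
- 60-minute repeats: tests at 0, 60 and 120 min, so at most 3 per excursion if Reference values are also above 240 mg/dL and the 2-hour stop applies. That gives 0–9 per subject, or 0–72 over 8 subjects.

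As a minor edit, item 13A should state at least hourly vital signs during closed loop (time 5–29 hours), or say that 4-hourly is only the recording interval. If staff now check only every 4 hours, the first option adds up to 24 − 6 = 18 sets per subject.
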